- Participants must have adequate organ function within 28 days of registration, defined as follows: - Absolute neutrophil count $\geq 1,500/\mu\text{L}$ - Platelets $\geq 100,000/\mu\text{L}$ - Hemoglobin $\geq 9\text{ g/dL}$ - Serum creatinine $\leq 1.5 \times$ upper limit of normal (ULN) - Total bilirubin $\leq 1.5 \times$ ULN (≤ 2.0 in patients with known Gilberts syndrome) OR direct bilirubin $\leq 1 \times$ ULN - Aspartate aminotransferase and alanine aminotransferase $\leq 2.5 \times$ ULN unless liver metastases are present, in which case they must be $\leq 5 \times$ ULN
- Participants receiving corticosteroids may continue as long as their dose is stable for at least 4 weeks prior to initiating protocol therapy.
- Participant must agree to not donate blood during the study or for 90 days after the last dose of study treatment.
- Female participants of childbearing potential must have a negative serum pregnancy test within 14 days prior to registration. Females of non-childbearing potential is defined as follows (by other than medical reasons): - ≥ 45 years of age and has not had menses for >1 year, post-hysterectomy, post-bilateral oophorectomy, post external beam radiation of 6 Gy to the pelvis, or post-tubal ligation.
- Participants must agree to not breastfeed during the study.
- Participants must be able to understand the study procedures and agree to participate in the study by providing written informed consent
- Participants must be eligible for chemoradiation treatment in the opinion of the treating investigator.
- Participants who are HIV+ must have CD4 counts $>200/\text{dL}$ and demonstrate documented Highly active antiretroviral therapy (HAART) compliance m.
- Participant must have CT (chest/abdomen/pelvis) or PET-CT, within 56 days of registration.
- Participants must be newly diagnosed.
- Standard chemoradiation using external beam radiation therapy

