J6. Consent Capacity - Adults who lack capacity

Will Adult subjects who lack the capacity to give informed consent be enrolled in the research?

No

J7. Prisoners

Will Prisoners be enrolled in the research?

No

Section K: Research Related Health Information and Confidentiality

Will research data include identifiable subject information?

Yes

Information from health records such as diagnoses, progress notes, medications, lab or radiology findings, etc.

Yes

Specific information concerning alcohol abuse:

No

Specific information concerning drug abuse:

No

Specific information concerning sickle cell anemia:

No

Specific information concerning HIV:

No

Specific information concerning psychiatry notes:

No

Demographic information (name, D.O.B., age, gender, race, etc.):

Yes

Full Social Security #:

No

Partial Social Security # (Last four digits):

No

Billing or financial records:

No

Photographs, videotapes, and/or audiotapes of you:

No

Identifiable biospecimens

Yes

Other:

No

At what institution will the physical research data be kept?

BCM

How will such physical research data be secured?

Secure storage

At what institution will the electronic research data be kept?

BCM

Such electronic research data will be secured via BCM IT Services- provided secured network storage of electronic research data (Non-Portable devices only):

Yes

Such electronic research data will be secured via Other:

No

Will there be anyone besides the PI, the study staff, the IRB and the sponsor, who will have access to identifiable research data?

No

Please describe the methods of transmission of any research data (including PHI, sensitive, and non-sensitive data) to sponsors and/or collaborators.

A Data Safety Monitoring Committee will review data for unanticipated adverse events. There is currently no plan to share research data with non-BCM personnel. For data to be transmitted between study personnel will be transmitted via BCM's encrypted/secure email system. All personnel are BCM employees and therefore have access to the BCM secure network. Any data files with patient information will be password protected and stored on the secure BCM server to ensure patient data security.

Will you obtain a Certificate of Confidentiality for this study?

No

Please further discuss any potential confidentiality issues related to this study.

All treatments will take place at BCM affiliated facilities, so no potential confidentiality issues are anticipated.

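### The CD4 limit in the HIV inclusion criterion is written per decilitre, so read literally it screens out practically no HIV-positive patient on CD4 count

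*Protocol*

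**What the plan says.** Section F1 (Design, Inclusion Criteria) of the protocol has one criterion for HIV-positive patients. It has two parts, and both must be met: "Participants who are HIV+ must have CD4 counts" above 200/dL, "and demonstrate documented Highly active antiretroviral therapy (HAART) compliance".

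The same list sets two other limits on blood cell counts, both per microlitre: "Absolute neutrophil count" of at least 1,500 and platelets of at least 100,000. The decilitre appears elsewhere in the list only for hemoglobin, in g/dL, which is a mass concentration and not a cell count.

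Section K (Research Related Health Information and Confidentiality) opens with the question "Will research data include identifiable subject information", answered Yes. In the checklist that follows, "Specific information concerning HIV" is answered No. Health-record information, including diagnoses, medications and laboratory findings, is answered Yes.

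**The concern.** The CD4 limit decides who may enter. Under Section J2, research coordinators assess patients for eligibility, and they work from this text. If they apply it literally, the CD4 part does nothing. If they silently read it in another unit, they apply a rule that the approved protocol does not state. Neither is satisfactory in a trial of a vaccine given with immune-modulating drugs, where CD4 is also one of the immune markers named in the corollary objective in Section D.

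A smaller matter goes with it. To show that an HIV-positive participant met the criterion, someone must document HIV status, a CD4 count and HAART compliance. The No in Section K sits awkwardly with that.

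**Working it through.** **Inputs.** All come from the Section F1 inclusion list: CD4 limit above 200/dL, neutrophil limit 1,500 per microlitre, platelet limit 100,000 per microlitre. The only other input is the unit conversion: 1 dL = 100 mL = 100,000 microlitres.

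**Step 1: the written limit in the unit of the other counts.**

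200 per dL ÷ 100,000 microlitres per dL = 0.002 cells per microlitre.

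**Step 2: who fails it.** Each CD4 count per microlitre is multiplied by 100,000 and compared with 200 per dL.

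| CD4 per microlitre | CD4 per dL | Above 200/dL? |
|---|---|---|
| 0 | 0 | No |
| 1 | 100,000 | Yes |
| 10 | 1,000,000 | Yes |
| 50 | 5,000,000 | Yes |
| 100 | 10,000,000 | Yes |
| 199 | 19,900,000 | Yes |
| 201 | 20,100,000 | Yes |

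Of the counts tried, only zero fails. The CD4 part therefore separates practically nobody.

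**Step 3: size of the discrepancy.** The same numeral read per microlitre would be 200 × 100,000 = 20,000,000 per dL, which is 100,000 times the written limit. This is for scale only and does not say what the limit ought to be.

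**Step 4: comparison within the list.** On the per-decilitre scale the neutrophil limit is 1,500 × 100,000 = 150,000,000 per dL. Next to that, a CD4 limit of 200 per dL is out of scale. The CD4 line is the only cell count in the list not given per microlitre.

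**Step 5: what the rest of the criterion does.** The HAART part is joined by *and* and contains no unit. An HIV-positive patient without documented compliance is excluded whatever the CD4 count. It is not a CD4 limit, though, and does not replace one.

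**Step 6: Section K beside Section F1.** Section F1 needs three facts on record for an HIV-positive participant: HIV status, CD4 count and HAART compliance. Section K says No to HIV-specific information but Yes to diagnoses, medications and laboratory findings, the kinds of record in which those facts would be found. The two sections do not flatly contradict each other, but they leave it unclear whether this evidence may be kept in the research data.

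**The case against.** The best case against the point is that this is a slip any clinical team would recognise. The two neighbouring cell counts are per microlitre, and it is hard to picture staff enrolling a patient with a handful of CD4 cells per microlitre because the line says dL. The line also ends in a stray letter, so the unit could be a fault of text extraction. Other criteria act as partial barriers too: the neutrophil and platelet limits, the investigator's judgment that the patient is eligible for chemoradiation, and the exclusion of uncontrolled intercurrent illness. No calculation in the protocol depends on the line.

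Much of this is fair, and it limits the point without removing it. Staff may well read past the slip, but eligibility should not rest on their doing so. The microlitre symbol came through correctly for both other counts, which makes an extraction fault unlikely; a look at the source file would settle it. None of the other criteria states a CD4 limit.

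Three stronger readings are tempting, and the documents do not support them:

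- *The HIV criterion excludes no one.* This is true, practically, of the CD4 part alone. The HAART part still excludes patients without documented compliance.
- *HIV information will not be collected.* Section K is a confidentiality checklist about identifiable content of the research data. It does not say that HIV status or CD4 count will go unchecked at screening.
- *The progression-free survival comparison is weakened.* The documents give neither the expected number of HIV-positive participants nor the handling of HIV in the historical cohort, so no such effect can be shown or sized.

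**Conclusion.** The CD4 part of the HIV inclusion criterion is wrong as written. At 200/dL, or 0.002 cells per microlitre, it screens out practically no HIV-positive patient, and it differs by a factor of 100,000 from the same numeral in the unit used for the other cell counts. The conclusion rests on the printed unit being dL, as the available text shows; the conversion itself needs no assumption. That the unit is a slip is an inference from the neighbouring criteria, and only the study team can confirm what was meant.

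The consequence is confined to eligibility and its documentation. The target of 77 cervical cancer patients, the one-sided 10% alpha and the 24-month comparison with the historical control do not depend on this line. The Section K entry is a secondary inconsistency to be reconciled; it does not show that the criterion cannot be applied.

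**What to change.** 1. The study team should confirm the intended CD4 unit and value against its source, and correct the criterion in Section F1 so that its unit is consistent with the neutrophil and platelet counts in the same list. The choice of limit is the team's, and none is proposed here.
2. Reconcile the No for HIV-specific information in Section K with the need to document HIV status, CD4 count and HAART compliance. Either change the answer or state where the eligibility evidence will be held.

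The cost is one corrected line in the eligibility list and one form answer or clarifying sentence. No sample-size or analysis text needs to change. If HIV-positive participants have already been enrolled, their eligibility records should be checked against the confirmed criterion.

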
Section D: Purpose and Objectives

PRIMARY: The primary objective of the study is to determine the effect on 24 month progression free survival of intratumoral HPV vaccination with topical imiquimod and oral metformin for locally advanced cervical, vaginal, or vulvar carcinoma in conjunction with definitive whole pelvic radiotherapy with chemotherapy followed by brachytherapy. Although the clinical benefit of this combination of drugs has not yet been established, the intent of offering this treatment is to provide a possible therapeutic benefit, and thus the patient will be carefully monitored for tumor response and symptom relief in addition to safety and tolerability.

SECONDARY: Assess for unanticipated toxicity of the combination of intratumoral HPV vaccination with topical imiquimod and oral metformin when administered in conjunction with chemotherapy with whole pelvic radiotherapy for cervical or vulvar carcinoma. .

Corollary Objective: Study of specific immune markers and modalities by which the combination immunotherapy boosts the immune system and works in sync with the standard of care to enhance its effects. Immune biomarker assays will be performed in cervical swab and blood samples at the beginning, middle, and end of the treatment to measure the effects of treatment on several immune markers including: CD4, CD8, NK, TNF alpha and beta, IL2, HPV viral load, TGF Beta, Ki67, IgG. We will also do blood tests to test for IgG L1 and L2, E6 and E7 and a CBC. These markers were chosen to identify specific immune changes of the three treatment groups.

Section E: Protocol Risks/Subjects

E1. Risk Category

Category 2: Research involving greater than minimal risk, but presenting the prospect of direct benefit to the individual subjects.

E2. Subjects

Gender:

Female

Age:

Adult (18-64 yrs)

Ethnicity:

All Ethnicities

Primary Language:

English, Spanish

Groups to be recruited will include:

Asymptomatic patients with chronic conditions, healthy; Patients

Which if any of the following vulnerable populations will be recruited as subjects?

Vulnerable populations require special protections. How will you obtain informed consent, protect subject confidentiality, and prevent undue coercion?

E3. Pregnant woman/fetus

Will pregnant women and/or fetuses (as described in 45 CFR 46 Subpart B) be enrolled in the research?

No

E4. Neonates

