Will neonates of uncertain viability or nonviable neonates (as described in 45 CFR 46 Subpart B) be enrolled in the research?

No

E5. Children

Will children be enrolled in the research?

No

Section F: Design/Procedure

F1. Design

Select one category that most adequately describes your research:

u) Drug, Phase II, Single Center

Discuss the research design including but not limited to such issues as: probability of group assignment, potential for subject to be randomized to placebo group, use of control subjects, etc.

This window-of-opportunity study will be offered to all eligible patients undergoing chemoradiation for cervical, vulvar, or vaginal cancer, since it is an additional treatment anticipated to enhance the response to therapy. The treatment group will be compared to a historical control. We will evaluate the immune changes within the tumor microenvironment and validate why the combination immunotherapy study elicited such a robust immune response which led to complete resolution of the cancer, in comparison to the standard of care, chemoradiation. If the combination immunotherapy used together with chemoradiation elicits a more robust antitumor response, there is the potential that the addition of these FDA approved medications to chemoradiation could be a new standard of treatment for squamous cell carcinoma of the cervix and vulva.

Inclusion Criteria:

- Participants must have histologically confirmed locally advanced or metastatic cervical carcinoma (Stage IB2-IVB), vaginal, or vulvar carcinoma (Stage II-IVB), AND not be considered a primary surgical candidate. Patients offered neoadjuvant therapy may be enrolled if they respond and receive chemoradiation. • Participants must have measurable disease, per Recist criteria. See Section 12 (Measurement of Effect) for the evaluation of measurable disease.
- Radiological evaluation shall occur within approximately 30 days prior to enrollment initiation and start of radiation.
- Participants must have an Eastern Cooperative Oncology Group (ECOG) performance status of ≤ 2
- Participants must be ≥ 18 years of age

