HPV 9-valent recombinant vaccine (3 milliliters/approximately ½ teaspoon) will be injected into several locations on the tumor surface, using ½ half of the single dose vaccine diluted with saline solution.

If you have cancer of the vulva, the vaccine will be injected without placing the speculum.

Imiquimod cream will be applied to the surface of the tumor at the visit.

You will then receive ½ of the vaccine dose as a subcutaneous shot.

Following the visit, you will receive 6 small doses of imiquimod cream in individual packets. These are to be applied using a vaginal applicator 3 nights per week for the next 2 weeks.

If you have cancer of the vulva, the imiquimod cream will be applied directly on the tumor surface.

You will also receive metformin 500 mg tablets, which are to be taken by mouth twice daily for the next 2 weeks.

A PET/CT test will be performed at treatment completion (week 20), then PET/CT or CT chest/abdomen/pelvis 2 years post treatment. You will have follow-up visits with a physical exam including pelvic exam every 3 months up until 2 years.

Section G: Sample Size/Data Analysis

G1. Sample Size

How many subjects (or specimens, or charts) will be used in this study?

Local: 85 Worldwide: 85

Please indicate why you chose the sample size proposed:

The planned cohort size will be 77 primary cervical cancer patients, the number needed for the evaluation of improvement in time to progression-free survival, with up to 8 vulvar/vaginal cancer patients, since they are rare. Members of the protocol study team have completed a comprehensive review of local control outcomes for all women treated for a locoregionally advanced cervical cancer (bulky FIGO IB3- IVA) with chemoradiotherapy to include standard of care concurrent cisplatin at the Harris Health System. Twenty-four month progression-free survival for patients who presented with FIGO IIIA-IVA cervical cancer is 67%. Since this clinical trial is enrolling an advanced stage cohort, we estimate that PFS would be 67% with standard of care and we will consider the trial a success if PFS is better than 77% at 24 months. Employing a one-sample exponential hazard rate test, and using a survival time of at least 2 years, which is consistent with the follow up time of 2 years, a sample of 77 patients are needed (alpha=10%, one-tailed, history control PFS24 m=67% vs new PDA24m=77%). Similar results are obtained for a standard one-sample log-rank test. .

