J1. Waiver of Consent

Will any portion of this research require a waiver of consent and authorization?

No

J1a. Waiver of requirement for written documentation of Consent

Will this research require a waiver of the requirement for written documentation of informed consent?

No

J2. Consent Procedures

Who will recruit subjects for this study?

PI
PI's staff

Describe how research population will be identified, recruitment procedures, any waiting period between informing the prospective participant and obtaining consent, steps taken to minimize the possibility of coercion or undue influence and consent procedures in detail.

All patients undergoing chemoradiation for cervical, vaginal, or vulvar carcinoma at BCM sites (Smith Clinic and Dan L Duuncan Comprehensive Cancer Center - DLDCCC) will be identified as candidates by their Gynecologic oncology (Gyn Onc) providers at their initial visit and/or at tumor board presentation. All Gyn Onc providers are listed as investigators for this study and will be able to discuss the procedure with patients. Research coordinators will then evaluate the patients for eligibility for the study. The trial will be discussed with patients in the weeks before starting radiation and offered to them by the physician. A copy of the consent form will be provided and all efforts will be made to provide the patient with time to decide on the trial without delaying their standard of care treatments. It will be explained that this treatment is not required to receive standard chemoradiation, and that participation is completely optional and will not otherwise affect the standard care that they receive. We will discuss the rationale for the study based on case reports where these experimental treatments have cured a small number of patients. It will also be explained that the medications themselves are well known and widely used, with a known safety profile that is overall well tolerated.

Are foreign language consent forms required for this protocol?

Yes

Which of the following ways will you document informed consent in languages other than English?

A full-length informed consent document

J3. Privacy and Intrusiveness

Will the research involve observation or intrusion in situations where the subjects would normally have an expectation of privacy?

No

J4. Children

Will children be enrolled in the research?

No

J5. Neonates

Will non-viable neonates or neonates of uncertain viability be involved in research?

No

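### The 67% null and 77% success mark come from FIGO IIIA-IVA patients but are applied to cervical stages IB2-IVB, so stage mix alone can move the single-arm result, in a direction the protocol does not let one determine

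*Protocol*

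**What the plan says.** **Source of the null.** G1 describes a completed local "comprehensive review of local control outcomes for all women treated for a locoregionally advanced cervical cancer (bulky FIGO IB3- IVA"). From it, G1 reports PFS for one subgroup only: "Twenty-four month progression-free survival for patients who presented with FIGO IIIA-IVA cervical cancer is 67"%. The reason for using that figure is: "Since this clinical trial is enrolling an advanced stage cohort, we estimate that PFS would be 67% with standard of care". Success is PFS above 77% at 24 months, and 77 cervical patients are planned at one-sided alpha 10%.

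**Who is enrolled.** The inclusion criteria in F1 accept "histologically confirmed locally advanced or metastatic cervical carcinoma (Stage IB2-IVB"), subject to the condition "AND not be considered a primary surgical candidate". Recruitment is otherwise open. F1 says "This window-of-opportunity study will be offered to all eligible patients undergoing chemoradiation for cervical, vulvar, or vaginal cancer", and J2 identifies as candidates "All patients undergoing chemoradiation for cervical, vaginal, or vulvar carcinoma at BCM sites". No stage quota, cap or expected stage distribution is given.

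**Objective and analysis.** The primary objective in Section D is worded "for locally advanced cervical, vaginal, or vulvar carcinoma in conjunction with definitive whole pelvic radiotherapy" and does not mention metastatic disease. G2 compares PFS at 24 months with a historical cohort by Kaplan-Meier curve and log-rank test. It does not say which stages form that cohort.

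**The concern.** The trial has one arm, so the historical rate is its only control. That rate should describe what the enrolled patients would have experienced on standard chemoradiation alone. Here the enrolled range runs past the reference group at both ends: IB2-IIB are earlier stages than IIIA-IVA, and IVB is later.

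On the usual prognostic ordering, early-stage patients push PFS24 above 67% with no drug effect and IVB patients push it below, so the two partly cancel. A pass could then reflect a favourable stage mix, and a failure could hide a real effect behind an unfavourable one. Calling the cohort advanced-stage is an expectation that the eligibility criteria do not enforce.

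**Working it through.** **1. Stage ranges side by side**

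| Item | Cervical stages | Where |
|---|---|---|
| Eligible | IB2-IVB | F1, inclusion criteria |
| Historical review | IB3-IVA | G1 |
| Source of 67% | IIIA-IVA | G1 |
| Primary objective | locally advanced | Section D |
| Comparator in the log-rank test | not stated | G2 |

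IVB lies outside the review. So does IB2 if F1 and G1 use the same staging edition; neither names one.

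**2. The plan's own figure.** Exponential hazards are λ = -ln(S)/24. This gives λ0 = -ln(0.67)/24 = 0.01669 and λ1 = -ln(0.77)/24 = 0.01089 per month, a hazard ratio of 0.653. G1 states no power, so 77 cannot be strictly reproduced. If 80% power is assumed, events needed = (1.2816 + 0.8416)² / (ln 0.653)² ≈ 24.8.
- Null event probability at 24 months, 1 - 0.67 = 0.33: 24.8/0.33 gives 76 patients.
- Alternative event probability at 36 months, 1 - 0.77^1.5 = 0.324: 24.8/0.324 gives 77 patients.

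The figure of 77 is therefore not shown to be wrong. With 24 months of follow-up, its power is about 70-81% across test variants.

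**3. Pass rate if the null does not fit the mix.** Inputs: n = 77, exponential times, 24 months per patient, inactive treatment. Two readings of success are shown:
- one-sample log-rank, Z = (E - O)/√E > 1.2816, where E is the number of events expected at 67% (simulation);
- observed PFS24 above 77%. Since 0.77 × 77 = 59.3, this needs at least 60 of 77 (exact binomial).

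| True standard-of-care PFS24 of the mix | Log-rank passes | Observed above 77% |
|---|---|---|
| 65% | 5% | 1% |
| 67% | 9% | 2% |
| 70% | 22% | 8% |
| 72% | 35% | 15% |

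At a true 77%, power is about 74% on the log-rank reading and 49% on the observed-rate reading.

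**4. Assumed mixes.** None of the following stage-specific rates is in the protocol. Stages IB2-IIB are set at 70, 75 or 80%, IIIA-IVA at 67%, and IVB as shown. The PFS24 of the mix is the share-weighted average; for example, 0.25 × 70% + 0.75 × 67% = 67.8%.

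| Early share | IVB | PFS24 of mix | Log-rank passes | Observed above 77% |
|---|---|---|---|---|
| 25% | none | 67.8-70.3% | 12-24% | 3-9% |
| 50% | none | 68.5-73.5% | 15-47% | 5-23% |
| 25% | 10% at 30% | 64.1-66.6% | 3-8% | 1-2% |
| 50% | 10% at 30% | 64.8-69.8% | 4-21% | 1-7% |
| 25% | 10% at 50% | 66.1-68.6% | 7-15% | 2-5% |
| 50% | 10% at 50% | 66.8-71.8% | 9-34% | 2-14% |

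These are 18 mixes (six rows, three early-stage rates each). Some sit near the nominal rate, some well above it and some below. On the observed-rate reading, 15 of the 18 stay under 10%.

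**5. A stage-specific null.** Each patient's expected events come from her own stage group, no IVB is counted, and the hazard ratio of 0.653 applies in both groups. The inactive pass rate returns to about 9% in all six mixes. Power at n = 77 with early-stage PFS24 of 70, 75 or 80% is 73, 72 or 70% at a 25% early share, and 72, 69 or 66% at a 50% share.

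**The case against.** Several points on the other side carry weight.

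- **The comparator may be broader than IIIA-IVA.** G2 names only a historical cohort. If the whole IB3-IVA review is used, much of the early-stage mismatch leaves the log-rank test. This stands, but 67% and 77% remain IIIA-IVA figures, and IVB remains uncovered.
- **The inflation depends on how success is read.** On the observed-rate reading the pass rate stays below 10% for most assumed mixes. This also stands. Stage mix still multiplies the 2% baseline about threefold at a true 70% and sixfold at 72%.
- **Other criteria limit the extremes.** Surgical ineligibility may restrict early stages. Definitive pelvic radiotherapy, fitness for chemoradiation and newly diagnosed disease may restrict IVB. None of these excludes either group, and the criteria provide for liver metastases and treated brain metastases.
- **A separate analysis plan could add stage adjustment.** It could, but the null, the success mark and the eligible stages are already fixed in this protocol and do not describe the same patients.

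A reader might infer that 67% is simply too low and that the trial leans towards false success. The document does not support that: IVB pulls the other way, and neither the mix nor the rates are given. The 30-40% persistent or recurrent figure in Section C does not settle it, having no time point and no stage split.

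**Conclusion.** The concern holds as a mismatch of populations. The 67% null and the 77% mark come from a narrower stage range than the 77 patients to whom they are applied, and no provision in the protocol closes the gap. The text is explicit, so confidence in the mismatch is high.

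The consequence is less certain. A shift of three to five percentage points in the true standard-of-care PFS24 moves the pass rate of an inactive treatment several-fold under either reading of success. Whether such a shift will occur, and in which direction, cannot be determined from the document. All stage-specific rates and shares used above are assumptions.

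Two stronger readings should not be drawn. The sample size of 77 is not shown to be wrong, and it is not established that the primary log-rank comparator is restricted to IIIA-IVA. This should be fixed before the result is interpreted; it does not by itself invalidate the design.

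**What to change.** 1. Name the historical cohort in G2, and state the staging edition used in F1 and G1.
2. Match the primary null to the stages analysed. In the one-sample log-rank test, take each patient's expected events from her stage group in the completed review (IB3-IIB or IIIA-IVA), and state success relative to that null.
3. Report stages that the review does not cover (IVB, and IB2 if applicable) separately, as G1 already does for vulvar and vaginal cancer.
4. Restate power: about 66-73% at 77 patients if early-stage PFS24 is 70-80% and the early share is 25-50%.
5. Reconcile the admission of IVB in F1 with the locally advanced wording of the primary objective in Section D.

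The cost is a protocol amendment, a small loss of power, and patients in uncovered stages falling outside the count of 77. It also needs IB3-IIB PFS from the review. G1 describes that review as one of local control and reports PFS only for IIIA-IVA, so the figure may not be available.

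If it cannot be extracted, keep 67% and 77%, state the success conclusion for IIIA-IVA only, and give that subset's power without requiring more patients. That power is about 64% if 75% of the 77 are IIIA-IVA (58 patients) and about 51% if half are (39 patients).
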